7.3.6 Reporting Process

Adverse events may be submitted on FDA Form 3500A, the HICCC DSMC Serious Adverse Event Reporting Form, or in a narrative format.

8.0 STATISTICAL ANALYSIS PLAN

8.1 Statistical Analysis Plan Summary

8.1.1 Primary Endpoint

The primary endpoint for this study is pathological complete response (pCR) defined as no invasive disease within an entirely submitted and evaluated gross lesion, and histologically negative nodes (T0N0). The **primary hypothesis** of this study is that combination induction and maintenance therapy including immunotherapy and chemotherapy will result in increased efficacy compared to historical use of chemotherapy alone. This will be achieved by comparing the pathological complete response (pCR) rate at the time of surgery following 3 cycles of pre-operative chemotherapy (with 4 cycles of pembrolizumab) to historical controls. Previous studies have reported low rates of pCR following neoadjuvant therapy with chemotherapy alone for gastric cancer (3% in the FNCLCC and FFCD study⁵ and 0% reported in the MAGIC study²). Although this is an uncommon finding this novel combination and increase pre-op dosing may increase the pCR rate to 15% or more. Assuming that 28 out of the 38 patients will be evaluable for pCR, we estimate that with 28 patients we will have 80% power to detect an increase in pCR rate from 3% to 15% with a one-sided binomial test with an actual alpha of 0.05. We reject the null that the pCR rate is 3% or less if 3 or more out of the 28 patients respond.

8.1.2 Secondary Endpoint

The secondary endpoints are ORR, DFS and OS. DFS is defined as time from Cycle 1 Day 1 treatment administration to the first documented event of: disease progression, disease recurrence following surgery (preferably biopsy proven), or death- whichever occurs first. Overall Survival (OS): time from Cycle 1 Day 1 treatment administration to death due to any cause.

The secondary hypothesis of this study is that combination therapy with immune checkpoint blockade and chemotherapy used in the perioperative period will eradicate micrometastatic disease and improve disease free survival (DFS).

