1.1 PROTOCOL SYNOPSIS

Title	Phase II study of combination chemotherapy and immune checkpoint blockade with Pembrolizumab in the perioperative and maintenance treatment of locoregional gastric or GE junction adenocarcinoma.
Short Title	Perioperative chemotherapy and pembrolizumab in locally advanced gastric cancer (Merck Internal Reference: MISP 52339)
Protocol Number	AAAQ9871
Phase	Phase II
Methodology	Single arm, multi-center, Phase II study with interim safety analysis
Study Duration	30 months (for efficacy results)
Study Centers	Columbia University Medical Center, New York; Weill Cornell Medical Center, New York; Washington University in St. Louis, St. Louis; Rhode Island Hospital/Lifespan Cancer Institute, Providence, Rhode Island
Objectives	
Primary Objective:
 
 1. To evaluate the efficacy of combination therapy with immune checkpoint blockade and chemotherapy as determined by the pathologic complete response rate (pCR). Pathological complete response is defined as no invasive disease within an entirely submitted and evaluated gross lesion, and histologically negative nodes. 
Secondary Objectives:
 
 2. To determine the efficacy of combination therapy with immune checkpoint blockade and chemotherapy by overall response rate (ORR), and used in the perioperative period in eradicating micrometastatic disease as measured by disease free survival (DFS) and overall survival. 3. To compare paired tissue and serum samples (pre-treatment and post-treatment) from individually treated patients to explore the immune effects of combination therapy and predictors of response as determined by IHC, flow cytometry, and genomic analysis of tumor and immune cells 
Exploratory Objective:
 
 1. To determine if pathologic complete response (pCR) rate correlates with recurrence free survival (RFS)

Number of Subjects	There will be an estimated 38 patients enrolled in this protocol. We estimate that at least 28 subjects will proceed to surgery and be evaluable for the primary outcome of pCR. All subjects will be available for the secondary analysis of ORR, DFS, and OS.

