7.2.2.7.2 Tumor Imaging During Trial

The first on-study imaging assessment will be performed 11 weeks after Cycle 1 Day 1 (78 days +/- 14 days) and will be used to assess response to chemotherapy and eligibility for surgery. Imaging may be conducted prior to Cycle 4 dosing (of Pembrolizumab) if clinically indicated as assessed by local routine practice. Subsequent imaging will be performed

following surgical resection and will begin within 7 days of Cycle 5 day 1 (first post-operative cycle) which is expected to not be later than 8 weeks from the time of surgery (65 days +/- 14 days). Beginning from the first post-operative scan, subsequent tumor imaging will be performed every 12 weeks (+/- 7 days).

Imaging should continue to be performed until whichever one of the following occurs first:

- disease progression limiting a subject from surgical resection
- recurrence of disease following surgical resection
- completion of study treatment
- withdrawal of consent
- death
- end of study

Imaging should follow calendar days and not be delayed for any dose interruptions that may occur (except for delays post-operatively).

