7.2.5.2.1 Pre-operative Treatment Period

This will begin on Cycle 1 Day 1 and as outlined will include 4 cycles of therapy. The first 3 cycles will consist of combination chemotherapy and Pembrolizumab and the 4th cycle will consist of study treatment alone with Pembrolizumab. Based on previous studies it is anticipated that subjects will proceed to surgery between 4-6 weeks following completion of perioperative chemotherapy (completion of cycle 3). The pre-operative treatment period will complete once a subject proceeds to surgical exploration.

All subjects will remain on study if they have received a single dose of study medication, even if they did not complete the full course of pre-surgical chemotherapy or combination therapy.

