8.2.5 Measurement of Effect

8.2.5.1 Definitions

Evaluable for toxicity: All patients will be evaluable for toxicity from the time of their first treatment with Pembrolizumab.

Evaluable for primary outcome (pCR):

All subjects who receive a single dose of study medication and are eligible will be considered evaluable for the primary outcome of pCR. Patients who discontinue treatment prior to surgery due to reasons other than eligibility (e.g. disease progression, toxicity, or physician discretion) will be considered as not having achieved pCR. For secondary analysis, we will consider not evaluable those who do not have a pathology report for determination of pCR or discontinue treatment prior to surgery due to reasons other than disease progression and toxicity for the estimation of pCR rate.

Evaluable for secondary outcome (RR, DFS, or OS): All subjects who receive a single dose of study medication will be included in the assessment of ORR, DFS, or OS.

Evaluable for objective response: All patients included in the study must be assessed for response to treatment if they have measurable disease at baseline.

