8.2.5.3 Response Criteria

8.2.5.3.1 Evaluation of Target Lesions

Complete Response (CR): Disappearance of all target lesions. Any pathological lymph nodes (whether target or non-target) must have reduction in short axis to <10 mm.

Partial Response (PR): At least a 30% decrease in the sum of the diameters of target lesions, taking as reference the baseline sum diameters.

Progressive Disease (PD): At least a 20% increase in the sum of the diameters of target lesions, taking as reference the smallest sum on study (this includes the baseline sum if that is the smallest on study). In addition to the relative increase of 20%, the sum must also demonstrate an absolute increase of at least 5 mm. (Note: the appearance of one or more new lesions is also considered progressions).

Stable Disease (SD): Neither sufficient shrinkage to qualify for PR nor sufficient increase to qualify for PD, taking as reference the smallest sum diameters while on study.

Progressive Disease (PD): Appearance of one or more new lesions and/or unequivocal progression of existing non-target lesions. Unequivocal progression should not normally trump target lesion status. It must be representative of overall disease status change, not a single lesion increase. Although a clear progression of “non-target” lesions only is exceptional, the opinion of the treating physician should prevail in such circumstances, and the progression status should be confirmed at a later time by the review panel (or Principal Investigator).

Disease recurrence: is defined as PD (as above) or appearance of a new lesion following surgical resection. Evidence of recurrence will generally require biopsy confirmation and the time of recurrence will be the time that biopsy is positive. In situations in which a biopsy is not feasible or recommended by the treating physician or is declined by the subject, the evidence of recurrence will be confirmed by the review panel (or Principal Investigator).

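### The DFS definition has no event for locally unresectable disease without progression or for macroscopic residual tumour, so these patients count as disease-free until later progression or death; the likely effect on 24-month DFS is small.

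*Combined protocol and SAP*

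**What the plan says.** Section 8.1.2 starts DFS at Cycle 1 Day 1, with the tumour in place, and ends it at "the first documented event of: disease progression, disease recurrence following surgery (preferably biopsy proven), or death- whichever occurs first". Section 8.2.5.1 sets the population: "All subjects who receive a single dose of study medication will be included in the assessment of ORR, DFS, or OS". Resection is not a condition for entering the analysis.

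Section 8.2.5.3.1 defines the events. Progression in target lesions needs "At least a 20% increase in the sum of the diameters of target lesions", with an absolute increase of at least 5 mm. Otherwise it needs "Appearance of one or more new lesions and/or unequivocal progression of existing non-target lesions". Recurrence "is defined as PD (as above) or appearance of a new lesion following surgical resection".

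Section 7.2.5.2.1 allows for surgery that stops at exploration: "The pre-operative treatment period will complete once a subject proceeds to surgical exploration". No section says how a patient explored but not resected, or resected with gross tumour left behind, is handled for DFS, whether as an event, a date or a censoring rule.

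The synopsis calls DFS a key secondary efficacy outcome. Section 8.2.1 reports it by Kaplan-Meier as a median and a 24-month estimate, each with a 95% confidence interval. Section 8.1.3 uses 24-month DFS, alongside pathological complete response, to define good responders for the immune-profile comparison.

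**The concern.** Unchanged residual tumour is neither progression nor recurrence under section 8.2.5.3.1. A patient whose local disease proves unresectable, with no growth and no new lesion, therefore stays event-free after surgery has failed. So does a patient with macroscopic tumour left after resection. Neither was ever free of disease. Section 4.2.3 gives the purpose of the outcome as eradicating micrometastatic disease and preventing recurrence once the tumour has been completely removed. For these patients the estimate does not measure that.

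Taken alone, the omission can only raise DFS, because the event comes later or not at all. It could also place a never-resected patient without progression among the good responders in section 8.1.3.

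The documents also disagree with each other. Section 4.2.3 describes time to recurrence or death, under the name recurrence free survival; section 8.1.2 adds progression and calls the endpoint DFS.

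**Working it through.** **The plan's own figures.** The documents give no design figure for DFS. The numbers 38 and 28 come from the pCR calculation in section 8.1.1. An exact binomial check of its rule (reject at 3 or more of 28; 3% versus 15%) gives power 81.3% and one-sided alpha 0.0506, close to the stated 80% and 0.05. That calculation has no bearing on DFS beyond supplying the numbers.

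**Inputs from the documents.** N = 38 (synopsis). On surgery the synopsis says: "We estimate that at least 28 subjects will proceed to surgery and be evaluable for the primary outcome of pCR". The allowance is therefore 38 − 28 = 10, or 26.3%. The DFS quantities reported are the median and the 24-month estimate (8.2.1).

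**Assumptions, not in the documents.**
- Surgery, or the decision against it, falls at month 3.5.
- k patients are locally unresectable or have gross residual tumour, without progression at that time.
- Their later progression or death is exponential, with median m months from surgery, and they are followed until it occurs.
- All other patients have exponential DFS with median M = 24 or 36 months.

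**Formula.** As written, an affected patient is still event-free at month t with probability 0.5^((t − 3.5)/m). With the event dated at surgery this is 0. The other patients contribute equally to both versions, so the overstatement at month t is (k/38) × 0.5^((t − 3.5)/m), whatever the value of M.

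**24 months.** The exponent is 20.5/m, so the factor is 0.0088 for m = 3, 0.094 for m = 6 and 0.306 for m = 12. Overstatement in percentage points:

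| k | m = 3 | m = 6 | m = 12 |
|---|---|---|---|
| 2 | 0.0 | 0.5 | 1.6 |
| 4 | 0.1 | 1.0 | 3.2 |
| 10 | 0.2 | 2.5 | 8.1 |

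For k = 10 and m = 9 it is (10/38) × 0.5^(20.5/9) = 5.4 points. The arithmetic limit is k/38 (5.3 points for k = 2, 10.5 for k = 4, 26.3 for k = 10), reached only if no affected patient progresses or dies by month 24.

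**Median DFS, M = 24 and m = 6.**
- k = 2: 22.6 months as written, 22.2 with the event at surgery.
- k = 4: 21.2 and 20.2.
- k = 10: 17.4 and 13.5.

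Across M = 24 or 36 and m = 3, 6 or 12, the shift is 0 to 1.2 months for k = 2 and 0 to 2.5 months for k = 4.

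**Scale.** As a rough guide to precision, the exact 95% interval for 19 of 38 is 33% to 67%.

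**What could lengthen m.** Section 7.2.2.7.2 times later scans from the first post-operative scan, so an unresected patient has no stated scan anchor. Section 5.8 does require disease-status follow-up for those who stop for reasons other than progression.

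**The case against.** Much of what looks like surgical failure is already covered. Imaging may end at "disease progression limiting a subject from surgical resection", and that is a DFS event as progression. Metastases first seen at exploration can be read as new lesions under section 8.2.5.3.1. Section 2.1 lets investigator assessment contribute to calling progression, and section 8.2.5.3.1 gives weight to the treating physician's opinion on non-target disease. All of this stands. The firm gap is local unresectability without growth or new lesions, plus macroscopic residual tumour. That metastases at exploration only can be read as events is itself a reason to state the rule and its date.

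A reader might infer that up to 10 of 38 patients are misclassified. The documents do not support that. Ten is a planning allowance. By the examples in section 8.2.5.1 it can include progression, already an event, and stops for toxicity or physician discretion, which are not surgical failures. Patients with gross tumour left after a resection did reach surgery and may lie outside the 10.

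A reader might also point to larger distortions at 6 or 12 months. The plan reports no estimate at those times.

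Finally, a reader might say that progression before surgery followed by complete resection is wrongly counted as failure. That is a debatable choice, not an error: section 5.8 lists confirmed radiographic progression among the reasons for stopping trial treatment. Removing those events would also move DFS upward, against the correction proposed here.

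**Conclusion.** The gap holds in its narrow form. For locally unresectable disease without progression and for macroscopic residual tumour, the definition records no event at surgery, and the resulting bias is toward higher DFS.

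Its size is unknown, because the documents give no rate for these cases. With 2 to 4 of 38 affected and a median of 3 to 12 months to later progression or death, 24-month DFS is overstated by about 0 to 3 points. The figure of about 5 to 8 points needs all 10 patients in the allowance to be affected and a median of 9 to 12 months; no part of the documents makes that plausible. Median DFS moves little for 2 patients and by up to about 2.5 months for 4 in the slowest scenario.

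These shifts are small beside the sampling error. DFS has no threshold, test or power statement, so no decision rule changes. The definition is usable but incomplete, and its name promises more than it measures. The point is a cheap improvement of low severity.

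**What to change.** In section 8.1.2:
- Rename the endpoint event-free survival, keeping Cycle 1 Day 1 as the origin and all dosed subjects as the population.
- Keep progression (including before surgery), recurrence and death as events, as now written.
- Add as events unresectable or metastatic disease found at exploration, and macroscopic residual disease. Date them at surgery, or at the decision of unresectability.
- State that patients not operated on for other reasons remain at risk.
- Report the current definition as a sensitivity analysis.

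Reconcile section 4.2.3 (recurrence or death) with section 8.1.2 (progression, recurrence or death), using one name throughout. Carry the revised endpoint into the 24-month good-response definition in section 8.1.3. Settle the rule before the outcome data are analysed.

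The cost is SAP and protocol wording. The inputs are in the operative and pathology records that surgery produces anyway. The downside is a slightly less favourable reported figure.

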8.1.3 Exploratory and Ancillary Studies

Gene expression profiles and IHC will be quantified as continuous variables and results will be compared between baseline and surgical specimens (pre therapy and post 12 weeks of combination therapy). We expect that some samples will be inadequate for analysis but anticipate 35 paired specimens. With 35 paired samples of pre and post specimens, we will have 80% power to detect a change of 0.50 standard deviation with a two-sided alpha of 0.05.

We will analyze changes in immune profiles between subjects (prior to and after treatment) using paired t-tests or non-parametric test if the data is not normally distributed. Moreover, we will compare immune profiles (using presence of TILs and PD-L1 expression among other measurements) between those who have a good response (defined as pathCR, or 24 month DFS) to those who do not have a good response. Given that we expect a small number of patients with pathCR, we will compare the data descriptively using summary statistics such as mean, median and ranges.

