2.0 TRIAL DESIGN

2.1 Trial Design

This is a non-randomized, multi-site, open-label trial of pembrolizumab and chemotherapy in subjects with gastric or gastroesophageal junction adenocarcinoma. Up to 38 subjects may be enrolled in a single cohort, for a sample of 28 evaluable subjects, to assess the efficacy of combination therapy with standard peri-operative chemotherapy in resectable gastric or GE junction adenocarcinoma. The trial was initiated at 2 sites and two additional sites were subsequently added to increase enrollment.

All study subjects will receive standard of care chemotherapy for 3 cycles prior to and 3 cycles following surgery in combination with Pembrolizumab with an additional cycle of Pembrolizumab (4 total) in the pre-operative period. Additionally, subjects will complete 12 months of maintenance Pembrolizumab (14 additional doses to complete 17 post-operative cycles) following completion of post-operative chemotherapy. The primary efficacy endpoint will be **pathologic complete response (pCR) rate** among all enrolled subjects. Recurrence or disease progression will be determined based on RECIST 1.1 and investigator assessment.

Adverse events will be monitored throughout the trial and graded in severity according to the guidelines outlined in the NCI Common Terminology Criteria for Adverse Events (CTCAE) version 4.0.(As referenced in Appendix 13.2)

After the end of treatment, each subject will be followed for 30 days for adverse event monitoring. Serious adverse events and Events of Clinical Interest (ECI) will be collected for 90 days after the end of treatment or 30 days after the end of treatment if the subject initiates new anticancer therapy, whichever is earlier. Subjects who discontinue treatment for reasons other than disease recurrence will have post-treatment follow-up for disease status until disease recurrence, withdrawing consent, or becoming lost to follow-up. All subjects will be contacted by telephone for overall survival until death, withdrawal of consent or the end of the study, whichever comes first.

[figure not shown]

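### The 80% power in 8.1.3 rests on 35 usable tissue pairs from at most 38 patients; the plan's own surgery estimate (at least 28) does not secure it

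*Combined protocol and SAP*

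**What the plan says.** SAP section 8.1.3 describes the paired tissue analysis: "results will be compared between baseline and surgical specimens (pre therapy and post 12 weeks of combination therapy". Each tissue pair therefore needs a surgical specimen. The same section allows for attrition and then gives a count: "We expect that some samples will be inadequate for analysis but anticipate 35 paired specimens". The 35 is thus the number left after inadequate samples are removed. The power claim follows: "With 35 paired samples of pre and post specimens, we will have 80% power to detect a change of 0.50 standard deviation", at a two-sided alpha of 0.05, using a paired t-test or a non-parametric test if the data are not normal. The section does not say whether the SD is that of the paired differences or of the raw measurements.

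Elsewhere the plan gives the patient numbers:

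- Section 2.1: "Up to 38 subjects may be enrolled in a single cohort, for a sample of 28 evaluable subjects".
- Synopsis (1.1), Number of Subjects: "We estimate that at least 28 subjects will proceed to surgery and be evaluable for the primary outcome of pCR".
- Section 8.1.1: "Assuming that 28 out of the 38 patients will be evaluable for pCR".
- Section 5.9: subjects who leave after receiving a dose are not replaced.
- Section 8.2.5.1: for the primary analysis every eligible dosed subject counts as evaluable for pCR. Only a further analysis drops those with no pathology result: "For secondary analysis, we will consider not evaluable those who do not have a pathology report for determination of pCR".

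On status, section 8.1.2 says "The secondary endpoints are ORR, DFS and OS", and the paired comparison sits under exploratory studies in 8.1.3. The synopsis lists the paired tissue and serum comparison among the secondary objectives.

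**The concern.** The pair count looks too high for the planned trial. Out of at most 38 patients, 35 usable pairs leaves 3 to be lost through progression, toxicity, withdrawal, cancelled surgery and poor samples combined. The synopsis commits only to a minimum of 28 who reach surgery and can be evaluated.

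This is the only power statement for the tissue comparison. If the number of pairs ends near the floor, a true 0.50 SD change would be missed about 28% of the time rather than 20%, before any sample is rejected. A null marker result could then be read as stronger evidence of no change than it is.

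**Working it through.** **Inputs.** Enrolment at most 38 (2.1). Anticipated usable pairs 35, effect 0.50 SD, two-sided alpha 0.05, paired t-test (8.1.3). At least 28 reaching surgery and evaluable (synopsis).

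**Room for losses.**

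- 35/38 = 92.1%, so 38 − 35 = 3 losses from all causes.
- 28/38 = 73.7%, so at the synopsis floor 38 − 28 = 10 patients do not meet the joint condition of surgery and evaluability.

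**Power formula.** For n pairs and a change of d SDs of the paired differences, the test statistic follows a noncentral t distribution with n − 1 degrees of freedom and noncentrality d√n. Power is the probability that its absolute value exceeds the 97.5% point of the central t.

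**The plan's own figure.** For n = 35 and d = 0.50, the noncentrality is 0.50 × √35 = 2.958, the critical value on 34 df is 2.032, and power is 82.0%. The stated 80% is reproduced, so the calculation is sound at 35 pairs.

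**Other pair counts, d = 0.50.**

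| Pairs | Power | Change detectable with 80% power |
|---|---|---|
| 35 | 82.0% | 0.49 SD |
| 34 | 80.8% | 0.495 SD |
| 33 | 79.5% | 0.50 SD |
| 32 | 78.2% | 0.51 SD |
| 30 | 75.4% | 0.53 SD |
| 28 | 72.3% | 0.55 SD |

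The smallest count with at least 80% power is 34 (34/38 = 89.5%).

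**Inadequate samples.** The documents give no rate, so 5% and 10% are assumptions.

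- From 28 resections: 28 × 0.95 = 26.6, so 26 whole pairs and 68.8% power; 28 × 0.90 = 25.2, so 25 pairs and 67.0%.
- To end with 35 usable pairs: 35/0.95 = 36.8, so 37 of 38 patients must be resected; 35/0.90 = 38.9, so 39, more than the 38 enrolled.

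**Choice of method.** The normal approximation needs 32 pairs for 80% power and gives 75.4% at 28. A Wilcoxon test, taking relative efficiency 0.955, gives 80.1% at 35 and about 70% at 28. At 28 pairs power is below 80% under each method.

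**If 0.50 SD means the raw SD.** With within-patient correlation ρ, the standardised change in the differences is d = 0.50/√(2(1 − ρ)).

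| ρ | d | Power, 35 pairs | Power, 28 pairs | Loss (points) |
|---|---|---|---|---|
| 0.3 | 0.423 | 68.0% | 57.8% | about 10 |
| 0.5 | 0.500 | 82.0% | 72.3% | about 10 |
| 0.7 | 0.645 | 96.0% | 90.9% | about 5 |
| 0.8 | 0.791 | 99.5% | 98.1% | 1.4 |
| 0.9 | 1.118 | >99.9% | >99.9% | about 0 |

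**The case against.** The best defence is that the synopsis figure is a minimum. Thirty-five lies between that floor and the cap of 38, and a team may reasonably use a cautious number for its primary endpoint and a more hopeful one for an exploratory analysis. This stands as far as it goes. A reader might infer that 8.1.3 and the synopsis flatly contradict each other, but the documents do not support that: both statements could turn out true. What remains is that a floor of 28 gives no ground for a forecast of 35, and no other passage supplies one.

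A reader might also take the 28 of 38 in 8.1.1 as a resection rate and conclude that 10 specimens will be lost. That goes too far. The 8.1.1 figure counts patients evaluable for pCR, and under 8.2.5.1 an eligible dosed patient is evaluable in the primary analysis whether operated on or not. Only the synopsis sentence mentions surgery, and it sets a joint condition: a patient could be operated on, provide tissue and still not be evaluable.

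A third tempting reading is that falling from 35 to 28 pairs always costs 5 to 10 points of power. On the raw-SD reading that is true for correlations of 0.3 to 0.7, but at 0.8 or above the loss is under 2 points and power at 28 pairs stays above 98%.

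Finally, the consequence is limited. No sample size, decision rule or stopping rule uses the 35.

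**Conclusion.** The concern holds as an unsupported, optimistic input to a power statement, not as an arithmetic error. The 80% is right for 35 pairs, but the plan's own surgery estimate does not secure 35. At the floor of 28, with every pair usable, power is 72% and the change detectable with 80% power rises from the stated 0.50 SD to 0.55 SD.

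These figures assume an exact two-sided paired t-test at 0.05 and that 0.50 SD means the SD of the paired differences. Section 8.1.3 does not say so, but its 80% reproduces on that reading. If the raw SD is meant, the size of the shortfall depends on a correlation that the plan does not give; the unsupported pair count remains either way.

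The point covers tissue pairs only. Correlative blood is drawn at screening, Cycle 4 and end of treatment and does not hinge on a surgical specimen. One further pressure on pairs, not counted above, is that section 2.1 waives resection tissue for complete or near-complete pathological responders. The primary endpoint and its decision rule are unaffected, and the severity is minor.

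**What to change.** In 8.1.3, base the pair count on the plan's own surgery estimate and name the SD. Suggested wording:

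*If 28 patients are resected and all give a usable pair, a two-sided paired t-test at alpha 0.05 has 72% power for a change of 0.50 SD of the paired differences and 80% power for 0.55 SD. At least 34 pairs are needed for 80% power at 0.50 SD. Inadequate samples would lower these figures.*

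If the raw SD was intended, the section should say so, state the assumed within-patient correlation and recompute the figures. If 35 pairs is kept, it should state the surgery rate and the sample-adequacy rate that produce it.

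The cost is a few sentences in the SAP and a slightly less favourable stated power or detectable change. Enrolment, procedures and the primary analysis do not change.
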